8.2. Patient Registration in the Siteman Cancer Center OnCore Database

Registrations may be submitted Monday through Friday between 8am and 5pm CST. Urgent late afternoon or early morning enrollments should be planned in advance and coordinated with the Washington University research coordinator. Registration will be confirmed by the research coordinator or his/her delegate by email within 1 business day. Verification of eligibility and registration should be retained in the participant's study chart.

All patients at all sites must be registered through the Siteman Cancer Center OnCore database at Washington University after the patient has been consented, prior to the baseline MRI scan.

8.3. Assignment of Participant ID

Each patient will be identified with a unique Participant ID for this study. The Participant ID will be based on the patient's Participant ID in the SURVIVE Registry, as well as the patient's enrollment number in the PROACT study. All data will be recorded with this Participant ID on the appropriate CRFs.

9. ADVERSE EVENTS AND REPORTING REQUIREMENTS

Only adverse events in relation to the study procedures will be documented and reported. These include adverse events occurring from the MRI scanner, SENC MyoStrain® Testing Software, or breach of confidentiality. Adverse events in relation to cancer diagnosis will not be recorded or reported. Recording of adverse events must be documented by the Participating Sites and entered into REDCap on a continuous basis.

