4. PROJECT DESCRIPTION

This study evaluates the impact of medical management of cardiotoxicity through early detection of at risk patients and management of with heart failure therapy to restore myocardial function.

SENC MyoStrain® testing will quantify changes in myocardial function at pre-defined intervals to detect the progression of cardiotoxic effects of chemotherapy and/or targeted treatment. Cancer treatment regimens such as anthracyclines, trastuzumab, taxanes, other agents, or combination of drugs, with or without concomitant Radiotherapy, have been shown to cause cardiotoxicity leading to heart failure. [22] [23]

MRI strain testing (SENC or HARP) has been shown to detect cardiotoxicity before systemic changes occur. MRI strain has been shown to detect abnormal myocardial function in cancer patients treated with high-dose anthracycline chemotherapy despite normal systolic function by traditional measures. [24] [25] Clinical utility of SENC strain testing is to evaluate risk of heart failure, immediate or delayed, for chemotherapy to reduce adverse cardiac events in cancer patients treated with anthracyclines or other drug therapy known to cause cardiotoxicity.

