Patient's will continue to undergo MyoStrain® MRI testing, regardless of study arm, at 1 month (\pm 2 weeks), 3 months (\pm 2 weeks), 6 months (\pm 2 weeks), 12 months (\pm 30 days), 24 months (\pm 30 days), and 36 months (\pm 30 days) after the baseline visit. In addition to the MyoStrain® testing, patients will also be asked to complete a brief patient satisfaction questionnaire at each PROACT time point. Patient's will already be completing the EQ-5D Questionnaire and the Cardiovascular Risk Assessment Questionnaire as part of the SURVIVE Registry protocol at the baseline, 6 month, 12 month, 24 month, and 36 month time points.

In addition to Myocardial Solutions, Inc. reviewing the cardiac MRI images, due to the multi-departmental nature of this study, sites may also choose to obtain a clinical read on the research cardiac MR images obtained on the short axis, which are the same images that would be obtained in a clinical MRI, and provide only the LVEF, LVEDV, and LVESV for all subjects, regardless of randomization arm, and those values may be uploaded to the patients' medical record, if permitted. Doing so would then allow patients' oncology team access to this information in lieu of obtaining additional testing (i.e. clinical cardiac MRI's, echocardiograms, etc.) to obtain this same information.

EXAMPLE OF GENERAL PRINCIPLES FOR CLINICAL DECISIONS WITH MYOSTRAIN® RESULTS:

- Worsening segment abnormalities, consider cardio-protective therapies.
- Advise oncology about developing toxicities.
- Enhance patient education (symptom awareness).

Figure 2 – Study Flow Diagram

PROACT Schedule of Events		Baseline	1 Month (±2 weeks)	3 Month (±2 weeks)	6 Month (±2 weeks)	12 month (±30 days)	24 month (±30 days)	36 month (±30 days)
PROACT Informed Consent		✓						
Inclusion/Exclusion Criteria Confirmation		✓						
MyoStrain® MRI Testing		✓	✓	✓	✓	✓	✓	✓
Randomization		✓						
Patient Satisfaction Questionnaire		✓	✓	✓	✓	✓	✓	✓

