9.4.6. Timeframe for Reporting Required Events

Adverse events will be tracked from time of consent to the last study visit. For the purposes of this protocol, adverse events collected and documented on CRFs include adverse events occurring from the MRI scanner, SENC MyoStrain® Testing Software, or breach of confidentiality.

All incidences of noncompliance and protocol exceptions will be tracked from the time of IRB approval, at the coordinating center, or site initiation at the participating centers, until the close of the study.

For more information on adverse event definitions and classifications and reporting requirements, please visit: <https://www.hhs.gov/ohrp/regulations-and-policy/guidance/reviewing-unanticipated-problems/index.html>

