10.1.3. Data Safety and Monitoring Committee

In compliance with the Washington University Institutional Data and Safety Monitoring Plan, the Principal Investigator will provide a Data and Safety Monitoring (DSM) report to the Washington University Quality Assurance and Safety Monitoring Committee (QASAMC) semi-annually beginning six months after accrual has opened (if at least 5 patients have been enrolled) or 1 year after accrual has opened (if fewer than 5 patients have been enrolled at the 6 month mark).

The Principal Investigator will review all patient data at least every 6 months, and provide a semi-annual report to QASMC. The report will include:

- HRPO protocol number, protocol title, Principal Investigator name, and research coordinator name
- Date of initial HRPO approval, date of most recent HRPO approval/revision of consent, date of HRPO expiration, date of most recent QA audit, study status, and phase of study
- History of study including summary of substantive amendments; summary of accrual suspensions including start/stop dates and reason; and summary of protocol exceptions, error, or breach of confidentiality including start/stop dates and reason
- Study-wide target accrual and study-wide actual accrual
- Protocol activation date
- Average rate of accrual observed in Year 1, Year 2, and subsequent years
- Expected accrual end date

- Objectives of protocol with supporting data and list of the number of participants who have met each objective
- Abstract submissions/publications
- Summary of any recent literature that may affect the safety or ethics of the study

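### Adverse-event recording covers only study procedures, which are the same in both arms; deaths, hospitalisations and other harms of changed management are not systematically collected by arm within PROACT

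*Combined protocol and SAP*

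**What the plan says.** **Scope of adverse events.** Section 9 sets the rule: "Only adverse events in relation to the study procedures will be documented and reported". The next sentence names the sources: "These include adverse events occurring from the MRI scanner, SENC MyoStrain® Testing Software, or breach of confidentiality". One class is expressly left out: "Adverse events in relation to cancer diagnosis will not be recorded or reported". Section 9.4.6 repeats the scope for the case report forms: "adverse events collected and documented on CRFs include adverse events occurring from the MRI scanner, SENC MyoStrain® Testing Software, or breach of confidentiality".

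**What the guided arm is for.** Section 4 describes early detection followed by "management of with heart failure therapy to restore myocardial function". Section 5.1 gives example principles for acting on the results, among them "Worsening segment abnormalities, consider cardio-protective therapies" and "Advise oncology about developing toxicities". The third primary objective (Sections 1.4 and 3) is the effect of MyoStrain imaging on medical management.

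**Monitoring report.** Section 10.1.3 lists the contents of the semi-annual report. They include accrual, amendments, protocol exceptions, confidentiality breaches, publications and "Objectives of protocol with supporting data and list of the number of participants who have met each objective". The list has no adverse-event summary and no table by arm.

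**Related provisions.** A clinical committee classifies cardiotoxicity status at each exam in both arms (Sections 1.5 and 11). Unanticipated problems are reported to the IRB (Sections 9.2.2, 9.4.1 and 9.4.3). Section 7.1 discusses MRI risks only.

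**The concern.** The trial does not randomise the scan. It randomises whether physicians see the MyoStrain values. Any true difference between arms, favourable or not, must therefore come from what physicians do with them. Section 11 expects 12.8 dysfunctional segments in the guided arm against 16.8 in the control arm at 6 months, and that difference can arise only through changed management.

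The plan measures the hoped-for benefit of those changes but sets up no matching record of their other consequences. The event types it does record come from procedures that both arms undergo alike. The trial could then report fewer dysfunctional segments in the guided arm with no table of deaths, admissions or treatment changes beside it. Whoever judges the guided strategy, during the trial or at its end, would lack the most basic safety description.

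**Working it through.** The plan gives no safety figure to reproduce, so the main check sets its provisions side by side.

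**Step 1. What differs between the arms (Sections 5.1 and 11).**

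| Element | Guided arm | Observational arm |
|---|---|---|
| MRI at baseline, 1, 3, 6, 12, 24 and 36 months | Yes | Yes |
| MyoStrain analysis of the images | Yes | Yes |
| MyoStrain values given to physicians | Yes | No |
| Volumes and LVEF available to physicians | Yes, from the company | Not from the company; through an optional site read |

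Exposure to scanner, software and data handling is the same. Disclosure, and the management that follows from it, is not.

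**Step 2. Where each kind of event would be captured.**

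| Event | Route in the plan | Systematic, by arm? |
|---|---|---|
| Scanner, software or confidentiality event | Sections 9 and 9.4.6 | Recorded, but exposure is equal by design |
| Worsening cardiac function | Committee classification at each exam | Yes |
| Unexpected problem, possibly related to participation, suggesting greater risk than known | Sections 9.2.2, 9.4.1 and 9.4.3 | No; case reports to the IRB |
| Known side effect of a treatment started after a result | None stated; would generally fail the unexpectedness test in 9.2.2 | No |
| Death or cardiovascular hospitalisation not attributed to study procedures | None stated | No |
| Start or stop of cardiac or cancer therapy | Medical history, including medications, is sent to the company (5.1); no visit schedule or dates given | Not shown |

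The schedule of events in Section 5.1 lists consent, eligibility, MRI, randomisation and a satisfaction questionnaire. It has no line for adverse events, admissions or therapy changes. Section 11 plans no comparison of adverse events.

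Section 1.5 expects most patients to have metastatic cancer, and follow-up runs to 36 months. Some deaths are therefore likely, and one attributed to the cancer falls under the express exclusion in Section 9.

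**Step 3. What collection could show at this size.** Section 5.7 gives 40 evaluable patients randomised 1:1, so 40 / 2 = 20 per arm.

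- Zero events in one arm: the one-sided 95% upper bound p solves (1 − p)^20 = 0.05. So p = 1 − 0.05^(1/20) = 0.139, or about 14%.
- Section 11 still carries 102 patients. At 51 per arm the bound would be 1 − 0.05^(1/51) = 0.057, or about 6%.
- Power of a two-sided 5% Fisher exact test at 20 per arm, under assumed event rates (the documents give none): about 17% for 5% against 20%, 24% for 10% against 30%, and 49% for 10% against 40%.

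Wider collection would support a description by arm, not a test.

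**The case against.** The strongest reply is that this is a small imaging-software study. The prompts in Section 5.1 are labelled as examples and ask physicians only to consider action. Section 7.2 leaves decisions to physicians using all available information. No treatment is mandated, so limiting events to the imaging procedure is a defensible choice. That stands in part: it rules out a claim that the plan tests a prescribed regimen without safety data. It does not explain why a trial whose stated objective includes the effect on management should not record what that management was or what followed. Section 7.2 also calls the measurements observational, which sits badly with Sections 4 and 5.1. The narrow scope fits only the observational reading, and the passages should be reconciled.

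Several stronger inferences are tempting and not supported:

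- *That all harms of the guided strategy go unseen.* Cardiac deterioration is captured in both arms, and the classification draws on symptoms and biomarkers as well as LVEF. EQ-5D is collected through the registry. The gap concerns other harms.
- *That such harms are banned from the record.* Both scope statements use inclusive wording, and a generous reading of software events might reach harm from acting on a wrong result. A serious unexpected harm could also reach the IRB. What is missing is systematic collection by arm.
- *That no linked source holds the data.* Every participant is in SURVIVE, whose protocol is not among the documents. It may record deaths or admissions. PROACT does not cite it for safety data.
- *That a probability can be put on missed events.* Any such figure needs an assumed event rate, and the chance of at least one event in one arm says nothing about imbalance between arms.
- *That recording events attributed to a study MRI report would solve the problem.* In an open-label trial where the company sends observational-arm physicians no results, that item would be ascertained unequally and could itself create an imbalance.

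**Conclusion.** The point holds in a limited form. Sections 9 and 9.4.6 confine documented adverse events to study procedures that are the same in both arms, while the randomised difference is disclosure meant to alter management. Cardiac status is covered and unanticipated problems have a reporting route. Deaths, hospitalisations and other harms of changed management are not systematically collected by arm within PROACT.

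The conclusion rests on the text of the sections cited and on SURVIVE being unseen. If the registry collects these items and PROACT means to use them, the remaining defect is that the plan does not say so. The gain from closing the gap is descriptive: at 20 per arm, even an arm with no events is compatible with a true rate of up to about 14%. This is a cheap improvement to oversight and interpretation, not a flaw that invalidates the efficacy comparison.

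**What to change.** Amend Sections 9 and 9.4.6 to record in both arms, at each scheduled visit and regardless of attribution:

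1. all deaths, with date;
2. all cardiovascular hospitalisations, with dates;
3. starts and stops of cardiac and of cancer therapy, with dates.

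Add the line to the schedule of events. Add a descriptive by-arm table to the semi-annual report in Section 10.1.3 and to the final analysis in Section 11, and state that it is descriptive only because there are 20 patients per arm. The table needs no MyoStrain values, so it does not disclose the results withheld in the observational arm. If SURVIVE already records any of these items, cite it as the source; Section 8.3 already bases the PROACT identifier on the registry identifier.

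**Cost.** One short CRF page at six follow-up visits for 40 patients, at most 6 × 40 = 240 pages, plus a protocol amendment. No extra procedure or staff is needed. After month 12 visits are a year apart, so some events will depend on recall or a check of medical records. The change proposes no treatment rule.

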9.1. Adverse Event Definitions

Term	Definition
Adverse Event (AE)	An unfavorable medical occurrence in a human subject including any abnormal sign, symptom, or disease.
Serious Adverse Event (SAE)	An adverse experience occurring that results in any of the following outcomes: 
 a. Death b. A life-threatening adverse experience

	
 c. Inpatient hospitalization or prolongation of existing hospitalization d. A persistent or significant disability/incapacity (i.e. a substantial disruption of a person's ability to conduct normal life functions) e. A congenital anomaly/birth defect f. Any other experience which, based upon appropriate medical judgment, may jeopardize the subject and may require medical or surgical intervention to prevent one of the outcomes listed above
Life-Threatening	An adverse experience that places the subject (in the view of the investigator) at immediate risk of death from the reaction as it occurred, i.e. it does not include a reaction that, had it occurred in a more severe form, might have caused death.

9.2. Attribution, Anticipation, Expectedness, and Grading of AEs

The terms for attribution, expectedness, and severity are defined as follows:

9.2.1. Attribution

Classification	Description
Definitely Related	The adverse event, incident, experience or outcome was definitely caused by the procedures involved in the research.
Probably Related	There is a reasonable probability that the adverse event, incident, experience or outcome may have been caused by the procedures involved in the research.
Possibly Related	There is a reasonable possibility that the adverse event, incident, experience or outcome may have been caused by the procedures involved in the research.
Unlikely Related	The adverse event, incident, experience or outcome was unlikely caused by the procedures involved in the research.
Unrelated	The adverse event, incident, experience or outcome was unrelated to the procedures involved in the research.

9.2.2. Anticipation

Classification	Description
Anticipated	Any incident, experience, or outcome that is anticipated to occur due to the research (i.e. procedures, investigational medication, etc.).
Unanticipated	Any incident, experience, or outcome that meets all of the following criteria: 
 a. unexpected (in terms of nature, severity, or frequency) given (a) the research procedures that are described in the protocol-related documents, such as the IRB-approved research protocol and informed consent document; and (b) the characteristics of the subject population being studied; b. related or possibly related to a subject's participation in the research; and c. suggests that the research places subjects or others at a greater risk of harm (including physical, psychological, economic, or social harm) related to the research than was previously known or recognized.

9.2.3. Expectedness

Classification	Description
Expected	Any adverse event that is a known or foreseeable risk associated with the procedures involved in the research or is an expected natural progression of any underlying disease, disorder, or condition.
Unexpected	Any adverse event occurring in one or more subjects in a research protocol, the nature, severity, or frequency of which is not consistent with either: 
 a. the known or foreseeable risk of adverse events associated with the procedures involved in the research that are described in (a) the protocol-related documents, such as the IRB-approved research protocol, any applicable investigator brochure, and the current IRB-approved informed consent document, and (b) other relevant sources of information, such as product labeling and package inserts; or

	b. the expected natural progression of any underlying disease, disorder, or condition of the subject(s) experiencing the adverse event and the subject's predisposing risk factor profile for the adverse event.
--	--

9.2.4. Grading

Grading refers to the severity of the adverse event. All adverse events will be graded using the revised NCI Common Terminology Criteria for Adverse Events (CTCAE) version 5.0. The CTCAE displays grades 1 through 5 with unique clinical descriptions of severity for each AE based on this general guideline:

Classification	Description
Grade 1	Mild; asymptomatic or mild symptoms; clinical or diagnostic observations only; intervention not indicated.
Grade 2	Moderate; minimal, local or noninvasive intervention indicated; limiting age-appropriate instrumental ADL (preparing meals, shopping for groceries or clothes, using the telephone, managing money, etc.).
Grade 3	Severe or medically significant but not immediately life-threatening; hospitalization or prolongation of hospitalization indicated; disabling; limiting self-care ADL (bathing, dressing and undressing, feeding self, using the toilet, taking medications, and not bedridden).
Grade 4	Life-threatening consequences; urgent intervention indicated.
Grade 5	Death related to AE.

For AE specific grading, please visit the following website to download a copy of the CTCAE version 5.0:

https://ctep.cancer.gov/protocolDevelopment/electronic_applications/docs/CTCAE_v5_Quick_Reference_8.5x11.pdf

9.3. Noncompliance and Exceptions

Term	Definition
Noncompliance	Failure to follow an applicable regulation or institutional policies that govern human subjects research or failure to follow the determinations of the IRB. Noncompliance may occur due to lack of knowledge or due to deliberate choice to ignore regulations, institutional policies, or determinations of the IRB.
Serious Noncompliance	Noncompliance that materially increases risks, that results in substantial harm to subjects or others, or that materially comprises the rights or welfare of participants.
Protocol Exceptions	A planned deviation from the approved protocol that are under the research team's control. Exceptions apply only to a single participant or a singular situation. Washington University central IRB pre-approval of all protocol exceptions must be obtained prior to the event for both the coordinating center and all participating sites. Participating sites must also follow their local IRB's guidelines for any submission that needs to be made to their local IRB.

9.4. Reporting Requirements

The entities providing oversight of safety and compliance with the protocol require reporting as outlined below. The Washington University Human Research Protection Office (HRPO) requires that all events meeting the definition of unanticipated problem or serious noncompliance be reported as outlined.

9.4.1. Reporting to the Human Research Protection Office (HRPO) at Washington University

The PI is required to promptly notify the IRB of the following events:

- Any unanticipated problems involving risks to participants or others which occur at WU or any BJH or SLCH institution that impacts participants or the conduct of the study.
- Noncompliance with federal regulations or the requirements or determinations of the IRB.
- Receipt of new information that may impact the willingness of participants to participate or continue participation in the research study.

These events must be reported to the IRB within **10 working days** of the occurrence of the event or notification to the PI of the event. The death of a research participant that qualifies as a reportable event should be reported within **1 working day** of the occurrence of the event or notification to the PI of the event.

9.4.2. Reporting to the Quality Assurance and Safety Monitoring Committee (QASMC) at Washington University

The PI is required to notify the QASMC of any unanticipated problem occurring at WU or any BJH or SLCH institution that has been reported to and acknowledged by HRPO as reportable. Unanticipated problems reported to HRPO and withdrawn during the review process need not be reported to QASMC.

QASMC must be notified within **10 days of receipt** of IRB acknowledgement via email to a QASMC auditor.

